## 8.0 Consent Process

Potential participants will be given a full description of the study procedures and asked to read and sign an IRB-approved informed consent form before any study procedures or assessments are conducted. Individuals who were recruited from the VA will also be required to read and sign a VA R&D –approved consent. Additionally, VA participants and their partners who are recruited from the VA will only be consented by study staff who have an active WOC or VA appointment. Informed consent will take place on the MUSC campus or via telehealth, using an IRB approved platform, such as Doxy.Me or RedCap. Initial eligibility screening will be conducted by the PI, Co-Is, Coordinator, or a trained research assistant by telephone or in person. If preliminary inclusion and exclusion criteria are met, staff will schedule an assessment appointment for the couple. In a private room apart from their partner, participants will be provided with a description of the nature and requirements of study participation, and asked to read and sign an IRB-approved consent form prior to beginning any study procedures. In the event of eConsent, the informed consent process will still take place privately. If couples do not have the ability to each have a private room for eConsent (within their residence(s), separate appointments may be arranged to maintain privacy and to meet with each individual partner separately. In the case of a VA consent, a VA consent document will either be mailed or emailed to the participant. PI/study team will use government furnished equipment to video call with the participant and go over the document. Once the document is signed, the participant will be asked to hold it up to the screen and a screenshot will be taken and saved for records. VA participants and their partners who are recruited from the VA will be given a VA Notice of Privacy Practices in addition to a copy of their consent.

## 9.0 Study Design / Methods

Figure 1 below illustrates the study design.

**Overview.** The proposed study is a 12-week, Stage-II, double-blind RCT examining the efficacy of combining oxytocin (40 IU) with ABCT in the treatment of AUD. A repeated measures design with two intervention arms will be used: ABCT + oxytocin compared to ABCT + placebo (Figure 1).

**General Procedures.** Following phone screening for preliminary eligibility, participants will complete a baseline assessment. In a private room apart from their partner, participants will be given a full description of the study procedures and asked to read and sign an IRB-approved informed consent form before any study procedures are conducted. In the event of telehealth, separate appointments will be made to meet with each individual partner separately. Consent will be conducted by trained staff (PI, Co-Is, Study Coordinator, or Research Assistant). Ineligible participants will be given treatment referrals as needed. During 1-2 baseline visits, participants will complete a breathalyzer or alcohol saliva test strip (to test current BAC), pregnancy test (for women), ethyl glucuronide (EtG) and phosphatidyl ethanol (PEth) testing, a history and physical (H&P) exam, urine drug screen (UDS), a battery of standardized self-report and interview measures (Table 1).. Note that for telehealth participants, biological specimens will not be collected, however, female participants will be required to take a pregnancy test (provided by study staff) and will be required to verbally confirm a negative result prior to continuing with any procedures. H&P exams will include a physical and neurological examination; orthostatic blood pressure and pulse measurements; and weight and BMI calculation. In the event of telehealth baseline appointment, biological measures will not be collected. Provided full eligibility criteria are met, participants will schedule visits to complete script development needed for the fMRI sessions and a fMRI session (described in the Neuroimaging Procedures section). Participants will then enter the treatment phase, which is a 12-week, double-blind, placebo controlled RCT during which they will receive weekly ABCT therapy sessions in combination with oxytocin or placebo (see Study Interventions and Procedures Section). Intranasal oxytocin has a half-life of approximately 3-4 hours and can be stored, refrigerated, for 2-4 weeks. If a participant misses multiple appointments, a new dose may be dispensed from IDS or Pitt Street Pharmacy. Participants will complete 3- and 6-month follow-up visits. AUD symptoms, relationship functioning, associated problems (e.g., depression), UDS, EtG, and adverse events will be assessed weekly. In addition, participants will be asked to complete a breathalyzer/alcohol saliva test strip while in the same room; after which they will be taken to separate rooms until it is time for therapy. PEth will be examined at baseline, weeks 6 and 12, and at both follow-up assessments. Blood samples will be refrigerated until sent to out for assay. Therapy sessions may be videotaped, with participant consent. In order to explore secondary outcomes such as the effects of treatment on within-session behaviors, we will employ observational coding to assess frequency of positive, negative, and alcohol change talk behaviors (using the SCCIT-A) in ABCT sessions 1, 4, 8, and 12.

**Table 1. Assessment Instruments and Timeline**

Instrument	Purpose	BSL	Weekly	Week 6	Week 12	3M F/U	6M F/U
Demographics Form	Characterize sample	X					
Mini Mental Status Exam (MMSE) 	Screen for cognitive deficits	PRN					
Quick Structured Clinical Interview for DSM-5 Disorders	Assess DSM-5 psychiatric disorders	X					
Concomitant Medications Form	Assess concomitant medications	X	X	X	X	X	X
Time Line Follow-[name] (TLFB) 	Primary outcome: AUD	X	X	X	X	X	X
Penn Alcohol Craving Scale (PACS  )	Assess alcohol craving	X	X	X	X	X	X
Alcohol Use Disorders Identification Test (AUDIT) 	Assess alcohol problems	X		X	X	X	X
Alcohol Dependence Scale (ADS) 	Assess domains affected by AUD	X			X	X	X
Readiness to Change Questionnaire (SOCRATES  )	Assess readiness to change AUD	X		X	X	X	X
Clinical Institute Withdrawal Assessment of Alcohol-Revised (CIWA-Ar) 	Assess alcohol withdrawal	X	X			X	X
Traumatic Life Events Questionnaire (TLEQ) 	Assess Trauma History	X					
PTSD Checklist (PCL-C) 	Assess PTSD symptoms	X			X	X	X
Beck Depression Inventory-II 	Assess depression	X	X	X	X	X	X
Cognitive Emotion Regulation Questionnaire; CERQ-Short 	Assess emotion regulation	X			X	X	X

Dyadic Adjustment Scale-short form (DAS) 	Primary outcome: Relationship functioning	X	X	X	X	X	X
Infidelity Assessment 	Assess Infidelity	X			X	X	X
Revised Conflict Tactics Scale 	Assess intimate partner violence	X		X	X	X	X
Reasons for Violence Scale 	Assess reasons for partner violence	X			X	X	X
Treatment Services Review	Monitor service utilization		X	X	X	X	X
Helping Alliance Questionnaire, Therapist and Client Version 	Asses therapeutic alliance		X	X	X		
Treatment Adherence	Assess homework compliance		X	X	X		
History of Head Injuries	Assess fMRI eligibility	X			X		
Drinking goals	Assess treatment goals for alcohol	X					
Coping Questionnaire	Assess coping skills	X					
Marijuana Motives	Assess marijuana use	X					
Visual Analog Scale (VAS)	Asses alcohol craving	X			X		
Telehealth Questionnaire	Asses telehealth				X		
Psychological Stress Associated with COVID-19 Crisis Questionnaire	Assess stress related to COVID-19	X					

BSL=Baseline. F/U = Follow-Up. BP=Orthostatic Blood Pressure. BMI= Body mass index.

**Telehealth:** Participants in this research study may choose to complete appointments via home-based telehealth (HBT) care (i.e., service delivery to patients in their homes using consumer-friendly, video-conferencing technology) which may likely enhance retention by directly circumventing financial and transportation barriers associated with traveling to MUSC/VA for in-person sessions. Further, telehealth allows the study team to recruit and enroll participants who are located outside of the state of South Carolina (inside continental US). HBT sessions will be delivered via standard desk, laptop computer, tablet, or smartphone running MUSC/VA approved applications. Participants who choose telehealth will be required to have their own computer, tablet, or smartphone; however, webcams will be provided to participants for these visits as needed. Participants will be mailed required materials such as alcohol saliva test strips, pregnancy tests, and medication. Separate appointments will be made with each partner for instances where study team needs to meet with each individual separately or privately.

Biological samples will not be collected for individuals participating in HBT care, however prior to the baseline appointment the study team will mail pregnancy tests and alcohol saliva strips to test for pregnancy and recent alcohol use. The alcohol saliva strip must read white (indicative of 0.00 BAC to validate the consent and prior to completing any study procedures. Further, prior to proceeding, females will be asked to take a pregnancy test and must provide verbal confirmation of a negative pregnancy test prior to proceeding with the baseline appointment and prior to administration of any study medication.

Female participants who complete appointments via telehealth will be required to take an at-home urine pregnancy test during those visits (provided by study team) and confirm a negative result (verbally and with photo of dipstick). The pregnancy tests used in this study are designed for at-home use, come with clear and simple instructions. In very rare and highly unlikely circumstances where the participant is unfamiliar with how to provide a urine sample or take an at-home pregnancy test, study staff can provide further instructions on how to provide a urine sample, how use the dipstick to test, and to differentiate between a positive and negative result. Ability and willingness to perform an at-home pregnancy test is required for telehealth female participants.

Study medication and other study required study materials will be shipped overnight from research pharmacy to participant's designated location at the agreed upon date using overnight shipping with contracted shipping company (FedEx, UPS) and with appropriate ice packs and temperature monitoring device as well as a signature requirement at delivery. Regarding all telehealth participants (including out of

state): Research participants will be asked to retrieve the study drug from their refrigerator at the beginning of each check-in video telehealth session with study staff. Participants will self-administer the medication while in view of the study staff on screen. Once medication is administered, participant will be instructed to return drug to their refrigerator prior to continuing with the remainder of the appointment.

**Optional Neuroimaging Procedures.** fMRI scans will be completed with participants and conducted at the MUSC Center for Biomedical Imaging (CBI; see Facilities and Resources), which houses a Siemens 3T Prisma MRI scanner (Siemens Medical, Erlangen, Germany). Neuroimaging sessions (Figure 5) will last approximately 60 minutes each and take place at baseline and week 12. After baseline, personalized imagery scripts will be developed for alcohol and neutral cues according to the manualized procedures described by Sinha and Tuit, which are currently being utilized in several of our team's ongoing federally-funded pharmacological trials for AUD. Participants will also develop a relationship conflict cue consistent with our past work. The VAS will be administered prior to, during, and after scanning to track perceived craving. Participants will be screened for metal using a self-report questionnaire and a handheld metal detector. Trained staff will position participants on the scanner bed with foam padding placed around their head to prevent motion. Participants will wear headphones to listen to the audio-recorded cues. During initial scanner tuning, localizing, and structural scanning, participants will be shown "relaxing" images (i.e., 20 scenic pictures, each displayed for 30 seconds). For co-registration and normalization of functional images, a high resolution T1-weighted MPRAGE anatomical image will be acquired with the following parameters: TR = 2300 ms, TE = 2.26 ms, flip angle = 8°, field of view = 256 mm, slice thickness 1.0 mm, 192 slices. The scanning planes will be oriented parallel to the anterior commissure–posterior commissure line.

**Compensation.** Each participant will each receive \$100 for completion of the baseline assessment visit, up to \$75 for completion of weekly ABCT sessions (on an escalating scale), and \$100 for each follow-up visit. Participants who are eligible and choose to complete the neuroimaging component of the study will also receive \$30 for the script development session and \$100 each for the pre-and post-treatment neuroimaging scans. Thus, participants who complete all study components may receive \$1,100 total. If obstacles of transportation prevent participation, the study team will offer bus, taxi, or mileage reimbursement as needed. Mileage reimbursement is available for individuals who travel more than 50 miles to Charleston. Reimbursement will be provided at the state-approved rate, and will be capped at 100 miles. Compensation types may include, but are not limited to: checks, cash, or gift certificates/cards.

## 10.0 Specimen Collection and Banking

Urine samples will be collected for pregnancy testing, urine drug screens, and ethyl glucuronide (EtG) testing. Blood samples will be collected from participants in this study for examining phosphatidyl ethanol (PEth). Blood will be drawn by trained personnel or the MUSC Research Nexus nursing staff and stored in the MUSC Fast Flow Lab until ready for processing. Only approved study staff will have access to data associated with specimens.

## 11.0 Data Management and Statistical Analysis Plan

**General.** Baseline clinical and descriptive characteristics will be examined and compared between treatment groups using chi-square tests, Fisher's exact tests, t-tests, or Wilcoxon rank sum tests, as appropriate. Baseline characteristics that are significantly different between treatment groups will be included as model covariates. The primary analysis will focus on end-of-treatment (i.e., the final three weeks of the treatment phase) outcomes using an intent-to-treat framework.

**Randomization.** Both partners in each couple will be randomized to the same drug condition in a one-to-one manner utilizing a randomized permuted block design. In order to ensure that the treatment groups are balanced with respect to alcohol consumption (TLFB), a stratified randomization process will be used.

We plan to use REDCap and VA REDCap for data capture and management. REDCap (Research Electronic Data Capture) is a software toolset and workflow methodology for electronic collection and management of research and clinical trial data (Harris et al., 2008; Harris et al., 2007). REDCap provides secure, web-based flexible applications, including real time validation rules with automated data type and range checks at the time of entry. Exports are made available for several statistical packages including SPSS, SAS, SATA, R and Microsoft Excel. The system allows the research team to create and engage respondents using a variety of notification methods.

REDCap data dictionaries can be distributed for reuse at multiple institutions. A library of data dictionaries is made available for standards-based data collection forms and validated instruments (Obeid et al., 2012). The underlying database is hosted in a secure data center at MUSC/VA, a secure environment for data systems and servers on campus, and includes redundancy, failover capability, backups and extensive security checks. The system has several layers of protection including, user/group account management, "Data Access Groups" which allow data to be entered by multiple groups in one database with segmented user rights for entered data, audit trails for all changes, queries and reports, and Secure Sockets Layer (SSL) encryption.

**Power and Sample Size.** This study is powered to detect moderate treatment group differences in percent days abstinent (PDA) and percent of days of heavy drinking (PDH), and relationship functioning as measured by the TLFB and DAS-7, respectively at end-of-treatment (weeks 9-12). Assuming 2-sided hypothesis testing and alpha levels of 0.05, we will have 80% power to detect treatment group differences with effect sizes of 0.6 in the presence of 30% attrition (n=70 couples) during the treatment phase. This approach is consistent with treatment group differences in PDA ( $d=0.59$ ) and PDH improvements ( $d=0.79$ ) in a prior ABCT trial (n=102), although we recognize that that trial compared individual therapy vs. ABCT (not ABCT  $\pm$  medication). In that study, PDA increased from  $34.98\% \pm 29.17\%$  to  $80.52\% \pm 27.75\%$  at the end of treatment in the ABCT group, and PDH decreased from  $56.83\% \pm 28.87\%$  to  $10.52\% \pm 22.16\%$  in the ABCT group. Incorporating an arcsine or other appropriate transformation to account for non-normality of these metrics will enable us to discern whether oxytocin enhances end of treatment PDA by an additional absolute 9% or greater (i.e., to 80.5% in the ABCT+ placebo group vs. 89.5% in the ABCT + oxytocin group) and whether oxytocin further decreases PDH by an absolute 6% or greater (i.e., to 10.5%

in the ABCT+ placebo group vs. 4.5% in the ABCT + oxytocin group). Another prior ABCT trial found that DAS-7 scores ( $21.1 \pm 6.7$ ) remain relatively constant throughout treatment. We will have 80% power to detect treatment group differences of 4 units of improvement in DAS-7 scores.

**Missing Data.** We will examine whether participants who complete treatment differ from those who drop out on key variables, and whether variables on which they differ interact with treatment group to affect outcome measures. Because participants will be randomized to treatment condition, it is unlikely that missing data will produce biased estimates of treatment effect, as observed and unobserved covariates will theoretically be balanced across treatment groups. In addition, less than 10% missing data generally has little impact on power and does not introduce bias, regardless of the missing data mechanism. If the percent missing data are greater than 10%, multiple imputation techniques will be used to examine the influence of missing data on our study findings. If data are missing not at random, propensity score methods will be considered for data imputation. In the propensity score method, first the distribution of the missing indicator variable given the observed data is modeled to derive a propensity score. Then observations are grouped on these propensity scores and an approximate Bayesian bootstrap imputation is applied to each group.

Hypotheses and statistical approaches for testing each are described below.

**Hypothesis 1:** The ABCT + oxytocin group will demonstrate significantly greater reduction in alcohol consumption from baseline to end of treatment as compared to the ABCT + placebo group (PDA and PDH measured by TLFB).

**Hypothesis 2:** The ABCT + oxytocin group will demonstrate significantly greater improvement in relationship functioning (measured by DAS-7) from baseline to end of treatment as compared to the ABCT + placebo group.

To test hypotheses 1 and 2, a general linear modeling (GLM) framework will be used, treating end-of-treatment (weeks 9-12) PDA, PDH, and DAS-7 scores as dependent variables (in separate models), and treating treatment group (ABCT + oxytocin vs. ABCT + placebo) as the primary independent variable. Baseline values for PDA, PDH, and DAS-7 will be included as covariates, along with other potentially significant baseline characteristics. Since PDA and PDH may exhibit non-Gaussian distributional forms and/or zero-inflation, alternative modeling strategies (e.g., arcsine or Box-Cox transformations, two-part Hurdle models) may need to be explored. Model fit will be compared by examination of Likelihood Ratio chi-square values. If transformations are necessary, back-transformations will be used in conveying the model results. Similar modeling strategies will be used for secondary exploratory outcomes (described below).

**Hypothesis 3a:** PFC-AMY functional connectivity after treatment will be greater in participants who receive ABCT+ oxytocin compared to those who receive ABCT + placebo.

**Hypothesis 3b:** Baseline PFC-AMY functional connectivity in response to alcohol vs. neutral cues will predict the magnitude of change in alcohol use (PDA and PDH measured by TLFB in the final 3 weeks of treatment).

**Hypothesis 3c:** Baseline PFC-AMY functional connectivity in response to relationship conflict vs. neutral cues will predict amount of change in relationship functioning (IP DAS-7 scores in the final 3 weeks of treatment).

For hypothesis 3, preprocessing and analysis of fMRI data will use FSL v 5.0^148. Preprocessing includes rigid-body head motion correction of EPI images within a run, high-pass temporal filtering (sigma = 150 seconds), geometric distortion correction, slice timing correction, spatial filtering (FWHM = 6 mm) and registration to the MNI standard brain template. 'fsl\_motion\_outliers' will be used to determine head motion outliers which will be used a covariate of no interest in statistical analysis (together with the 6 rigid-body

translation and rotation head motion parameters). The primary analysis of fMRI data will use psychophysiological interaction (PPI) modeling with a seed region defined in the right AMY region from the Harvard–Oxford probabilistic structural atlas thresholded at 50%. Time series will be extracted from each participant’s right AMY using ‘fslmeans’ after warping the AMY mask into each participant’s EPI space. This time series will serve as the physiological regressor for each run. The primary psychological regressors are based on the alcohol cue blocks in the alcohol run or the conflict cue blocks in the conflict run. The interaction between the primary psychological regressor for each run and the physiological regressor is the primary variable of interest.

fMRI analysis: To assess whether corticolimbic connectivity is modulated by oxytocin, the parameter estimate from the PPI interaction term will be extracted in the right and left inferior frontal cortex, opercular portion (IFC; -47, 18, 6) in each participant. The IFC regions-of-interest (ROI) are based on our preliminary study where the right AMY was functionally connected to the left IFC for the conflict cue, especially in women. In addition, the right IFC is strongly implicated in behavioral inhibition and may not be activated to the same degree in participants with AUD. The parameter estimates from the left and right IFC regions in each IP at pre- and post-treatment will be used in statistical analyses testing hypotheses 1 and 2 (described above). Because the hypothesized ROI may not yield the most robust response, we will also conduct a whole-brain, voxel-wise PPI analysis to identify PFC regions that show the greatest change in right AMY connectivity as a function of treatment. The voxel-wise PPI analysis will be conducted separately for each run (alcohol, conflict) but pre- and post-treatment sessions will be treated as a repeated measure. Group-level analyses will be carried out using FLAME 1 (FMRIB’s Local Analysis of Mixed Effects) to generate z statistical images for each interaction term in each run. The final statistical maps will be cluster thresholded at  $Z=2.33$ ,  $p = .05$  and will indicate which regions show the greatest change in connectivity with the right AMY as a function of treatment group.

**Exploratory Hypothesis 4:** The ABCT + oxytocin group will demonstrate significantly greater improvement in frequency of within-session behaviors (i.e., positive, negative, and alcohol change-talk behaviors measured by the SSCIT-A at sessions 1, 4, 8, and 12) as compared to the ABCT + placebo group.

To test exploratory hypotheses, a nonlinear mixed effects modeling framework will be used, where nonlinearity is likely to arise when participants transition from the treatment to follow-up phase. Separate models will be constructed for IPs and their partners. Time-specific outcome data will serve as dependent variables (in separate models, with treatment group being the primary independent variable of interest. Baseline values for PDA, PDH, DAS-7 and sex will be included as covariates, along with other potentially significant baseline characteristics. Models will include linear (and possibly non-linear) effects for time through the 6-month follow-up, allowing for changes in time effects to occur at end-of-treatment (i.e., using a regression ‘join-point’). Random subject effects will be incorporated to account for the fact that within-subject measurements over time are correlated with each other. Autoregressive covariance structures along with other structures (e.g., compound symmetry, spatial power) will be investigated, with final models based on Akaike Information Criterion. When examining outcomes involving counts (i.e., positive, negative, and alcohol change-talk behaviors), we will assume these variables follow Poisson and/or negative binomial distributions, accompanied by log-link functions within a generalized linear mixed models framework.

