**PROTOCOL TITLE: Oxytocin to Enhance Alcohol Behavioral Couple Therapy**

**PRINCIPAL INVESTIGATOR: [name].**

**ClinicalTrials.gov ID: Pro00082233**

**Document Date: March 8, 2022**

## 1.0 Objectives / Specific Aims

Identifying effective medications to treat alcohol use disorder (AUD) is a national public health priority. Combining pharmacological interventions with evidence-based behavioral treatments may help maximize and sustain AUD treatment outcomes. Alcohol Behavioral Couples Therapy (ABCT) is a manualized, evidence-based psychotherapy for the treatment of AUD that simultaneously targets relationship functioning, which is an important mechanism in the etiology, course, and treatment of AUD. While adaptive relationship functioning facilitates successful treatment engagement and outcomes, maladaptive relationship functioning interferes with AUD recovery and is a precipitant of relapse. Thus, ABCT employs cognitive behavioral techniques to (1) reduce alcohol consumption, (2) enhance partners' skills to facilitate recovery (e.g., communication, managing cravings together), and (3) enhance relationship functioning. Although ABCT is a highly efficacious treatment, there is room for improvement in outcomes, as more than half of ABCT patients report hazardous drinking episodes during treatment and a similar proportion fail to achieve abstinence.

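### Randomisation is stratified on baseline drinking, but no primary model commits to the stratum; if the DAS-7 model has no drinking term, its test may be modestly conservative.

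*Combined protocol and SAP*

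**What the plan says.** - **Randomisation (section 11.0, Randomization).** Couples are allocated 1:1 in permuted blocks, both partners to the same arm, and "a stratified randomization process will be used" to balance alcohol consumption by TLFB. The measure, the cut-points and the number of strata are not given.
- **Covariate rule (section 11.0, General).** "Baseline characteristics that are significantly different between treatment groups will be included as model covariates".
- **Primary models (section 11.0, text on testing hypotheses 1 and 2).** PDA, PDH and DAS-7 are analysed in separate general linear models. "Baseline values for PDA, PDH, and DAS-7 will be included as covariates, along with other potentially significant baseline characteristics". The stratum is not named here or anywhere else as a model term.
- **Power (section 11.0, Power and Sample Size).** "Assuming 2-sided hypothesis testing and alpha levels of 0.05", the plan states that "we will have 80% power to detect treatment group differences with effect sizes of 0.6 in the presence of 30% attrition (n=70 couples") and, for relationship functioning, "80% power to detect treatment group differences of 4 units of improvement in DAS-7 scores".

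**The concern.** When randomisation balances a factor, the treatment estimate no longer carries the chance variation due to that factor. A model that omits the factor leaves its variation in the residual, so the reported standard error exceeds the true one if the factor predicts the outcome. The test then rejects less often than its nominal level and power is lost.

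The drinking models contain a baseline drinking measure on any reading, so the exposed outcome is DAS-7, which is one of the primary outcomes in section 3.0. The protocol's rationale links the two domains ("While adaptive relationship functioning facilitates successful treatment engagement and outcomes", section 1.0), so some association between baseline drinking and later DAS-7 is plausible. The imbalance rule cannot be relied on to repair an omission, because stratification removes the imbalance that the rule looks for.

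**Working it through.** **Inputs from the documents.** Two-sided alpha 0.05; 100 couples randomised 1:1; 30% attrition, leaving 70 (35 per arm); DAS-7 difference of 4 units; SD 6.7 (the plan reports that "DAS-7 scores ( $21.1 \pm 6.7$ ) remain relatively constant throughout treatment").

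**Assumptions.** Two strata of about equal size, blocks of 4, attrition at random, and a partial correlation r between stratum and end-of-treatment DAS-7, given baseline DAS-7. The documents do not give r, so a range is shown.

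**1. The plan's own power figure.** Power = Φ(δ/SE − 1.96), with SE = 6.7 × √(2/35) = 1.602. This gives Φ(4/1.602 − 1.96) = Φ(0.537) = 70.5%, not 80%. For an effect size of 0.6 it is Φ(0.6/0.239 − 1.96) = 70.9%. About 80% is reached if baseline DAS-7 correlates 0.445 with the outcome: SE = 1.602 × √(1 − 0.445²) = 1.434 and power is 79.6%. The plan does not state such a correlation. The shortfall is a separate matter. The adjusted SE of 1.434 is used below because baseline DAS-7 is in the DAS-7 model on either reading.

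**2. Would the imbalance rule select the stratum?** In 24,000 simulated trials a chi-square test on the stratum was significant at 0.05 in none. A t-test on continuous baseline drinking was significant in about 0.1%.

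**3. Excess in the standard error under the own-baseline reading.** With exact balance, reported SE / true SE = 1/√(1 − r²). Random loss of 30 of 100 couples undoes part of the balance. The analysed 70 are a sample without replacement from a balanced 100, so 1 − 70/100 = 0.3 of the chance imbalance returns. The ratio becomes 1/√(1 − 0.7r²), and the actual type I error is 2 × [1 − Φ(1.96/√(1 − 0.7r²))].

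**4. Power for 4 units.** Without the stratum, power is Φ[(4 − 1.96 × 1.434)/(1.434 × √(1 − 0.7r²))]. With it, power is about Φ[4/(1.434 × √(1 − r²)) − 1.96].

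| r | SE excess, exact balance | SE excess, 30% attrition | Type I error, 30% attrition | Power without → with stratum |
|---|---|---|---|---|
| 0.1 | 0.5% | 0.4% | 4.9% | 79.7% → 80.0% |
| 0.2 | 2.1% | 1.4% | 4.7% | 80.0% → 81.2% |
| 0.3 | 4.8% | 3.3% | 4.3% | 80.4% → 83.2% |
| 0.4 | 9.1% | 6.1% | 3.8% | 81.0% → 86.1% |

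**5. Simulation check.** The design was 100 couples, 70 kept, baseline DAS-7 in the model at correlation 0.5, and 20,000 runs per value of r. At r = 0.2 / 0.3 / 0.4 the reported SE exceeded the empirical SE by 1.5% / 3.2% / 5.5%. Type I error was 4.7% / 4.2% / 3.8%. Power at 0.6 SD rose from 81.0% to 82.1%, 81.4% to 83.8% and 82.1% to 86.8%. Other runs gave about 0% / 3% / 5% for the SE excess. Differences of about a point are simulation error: with 6,000 runs the ratio has a relative standard error of about 1/√12,000 = 0.9%.

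**6. The other reading.** With continuous baseline drinking in the DAS-7 model instead of the stratum, reported SE / empirical SE was 0.99 to 1.01 across r = 0 to 0.5. Nothing material is left to correct.

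**The case against.** The strongest reply is that the plan already puts baseline drinking in the DAS-7 model. The covariate sentence lists three baselines with no word that pairs each with its own outcome, although the authors write 'respectively' in the power paragraph when they mean pairing. The text under Exploratory Hypothesis 4 uses nearly the same sentence, with sex added, for within-session behaviour counts. Those outcomes are none of the three, so only the list reading makes sense there. This reply has weight and makes the list reading the more likely one. It does not settle the matter. The covariate list repeats the outcome list in the same order after a statement that the models are separate, so a programmer could reasonably fit each outcome on its own baseline.

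Two stronger readings are tempting and are not supported.

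- A reader might infer that the plan can never bring the stratum in. That fits only the imbalance rule. The primary-model text separately admits other potentially significant baseline characteristics. That route has no stated criterion, so it permits the stratum without committing to it.
- A reader might infer that the DAS-7 standard error is too large as a matter of fact. That needs both the own-baseline reading and a stratum that predicts later DAS-7 beyond baseline DAS-7. The documents give no such correlation. The rationale in section 1.0 mainly describes relationship functioning affecting treatment outcome, not drinking severity predicting later relationship scores.

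It is also fair to say that the exact-balance figures (2.1%, 4.8% and 9.1%) overstate the effect once 30% of couples are lost.

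**Conclusion.** The gap is real but small and conditional. The trial stratifies on a factor that it neither defines nor commits to in any primary model, and its imbalance rule will in practice not select that factor. PDA and PDH are largely covered by their own baselines. The qualification is that the TLFB also yields drink counts (section 3.0), so with the stratifier undefined the coverage cannot be confirmed exactly.

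For DAS-7 the effect is close to nil if all three baselines enter every model. If only baseline DAS-7 enters, the reported SE is about 0-1%, 3% and 5-6% too large at r = 0.2, 0.3 and 0.4, and adding the stratum gains about 1 to 5 points of power. At r = 0.1 or below it makes no practical difference. These sizes rest on two equal strata, blocks of 4 and attrition at random. Any error is in the conservative direction, so it gives no reason to doubt a positive DAS-7 result.

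**What to change.** In the section 11.0 text on testing hypotheses 1 and 2, state that the randomisation stratum, or the continuous TLFB measure that forms it, is a fixed covariate in all three primary models, including DAS-7, whether or not it differs between arms. In the Randomization paragraph, name the TLFB measure, whose TLFB is used when both partners have AUD, and the cut-points. In the same edit, say whether each model takes all three baselines or only its own.

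The cost is one sentence for the covariate plus the definition of the factor, and one degree of freedom per extra stratum. With two strata and 70 couples, residual degrees of freedom in the DAS-7 model fall from 67 to 66. The stratum is known for every couple at randomisation, so no new data are needed.
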